4 STUDY DESIGN

4.1 OVERALL DESIGN

This multicenter, prospective, clinical trial will estimate the diagnostic yield of NewbornDx and rWGS testing and assess the clinical utility of genomic sequencing among high-risk infants with signs/symptoms consistent with a possible genetic disorder. The relative cost effectiveness of each testing method will be evaluated through simulation.

There are three components to this study:

1. Infants will undergo SOC diagnostic testing as well as NewbornDx and rWGS in parallel. Genetic sequences via NewbornDx and rWGS will be generated for the infant (proband) and when available, the biological parents, and analyzed together. NewbornDx and rWGS test results will be returned to the infant's clinician, medical record and parent/guardian. Those infants analyzed as a duo or trio will have a retrospective analysis done of only the infant's data to determine if the same result would have been obtained with and without parent samples. Clinical utility will be measured by clinician opinion and changes in the infant's care as a result of the genetic sequencing test results. QoL and medical resource utilization will be collected by parent survey monthly, until the infant is one year CGA.
2. A retrospective chart review of neonates with suspected genetic disorders completed at 3 sites, will be used to elucidate 1-year cost and health outcomes that would have been incurred in the absence of available NewbornDx and rWGS testing. The retrospective review will include 300 neonates born 12-18 months prior to the start of the study and performed under a separately submitted amendment to the central IRB. The cost and health outcome data will be used in an economic evaluation comparing NewbornDx, rWGS, and SOC over 1-year and a child's lifetime time trajectory.
3. A user-friendly clinical reference database will be developed to provide medical providers and families with information about genetic disorders, treatments, clinical trials and advocacy groups. A qualitative assessment of the clinical reference database will be conducted through surveys of clinicians involved in the infants' care. Once the database is completed and prior to implementation of the clinical reference database into this study, an amendment will be submitted to the IRB along with the survey.

Hypothesis #1: NewbornDx will detect at least 60% of the diagnoses identified by rWGS

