5 STUDY POPULATION

5.1 INCLUSION CRITERIA

In order to be eligible to participate in this study, an infant must meet all of the following criteria:

1. Documented informed consent from the parent/guardian
2. Signs/symptoms consistent with a possible genetic disorder including, but not limited to dysmorphic features, congenital anomalies, hypotonia, seizures, clotting, poor oral feeding skills
3. Admitted to a hospital (NICU, PICU, CVICU, inpatient floor) participating in this study at the time of enrollment (enrollment is not limited to the initial hospitalization after birth, it may occur during a readmission)
4. Less than one year CGA

There is not a requirement for clinical genetic testing prior to enrollment. However, enrollment in this study is not intended to replace targeted available genetic testing for specific suspected disorders that match the phenotype of the infant and make rWGS testing unnecessary. Examples include trisomies or a high likelihood of DiGeorge syndrome. In these cases, targeted genetic testing for a suspected disorder should be done prior to enrollment (e.g. DiGeorge syndrome and FISH for 22q11.2 deletion). Clinical genetic testing does not need to be completed prior to enrollment if there is more than one diagnosis on the differential diagnosis list. Other than these few situations, our goal should be to understand the role of utilizing rWGS and NewbornDx as a first line choice of testing.

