5.4 STRATEGIES FOR RECRUITMENT AND RETENTION

The anticipated number of infants to be screened is approximately 1200 in order for 400 infants to complete the study. Six US sites will recruit for this study. The parent/guardian(s) of all eligible infants will be approached. Enrollment is expected to include about 50% of each sex and proportions of each race that are represented in the general population in the multiple sites where the studies will be performed. The entire ICF will be translated into Spanish and short forms in other non-English languages will be utilized.

This study involves monthly follow-up from discharge home until 1 year CGA. In order to reduce the risk of lost to follow-up, study staff will have the parent/guardian(s) fill out the Follow-up Contact Information form at the time of transfer or discharge home. This form will document several methods of contact for the parent/guardian(s) and a family member or friend who would know how to reach the parent/guardian(s) if their contact information changes or they are unreachable. Then, the study coordinators will contact the family monthly until 1 year CGA to complete the parent surveys/interviews.

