9.4.3 ANALYSIS OF THE SECONDARY ENDPOINT(S)

Secondary Endpoints
1. One-year cost-effectiveness of NewbornDx and rWGS compared with SOC testing, from a societal perspective
2. Lifetime year cost-effectiveness of NewbornDx and rWGS compared with SOC testing, from a societal perspective

We will conduct an economic evaluation that will compare costs and health outcomes for infants with suspected genetic disorders who undergo: 1) traditional standard of care diagnostic testing, 2) NewbornDx, or 3) rWGS. One-year post-identification outcomes for NewbornDx and rWGS will be estimated from trial data, while outcomes for standard of care will rely on retrospective chart review. We will use simulation modeling to extend our projections beyond 1-year post identification to a lifetime time horizon.

In Trial Data Collection for NewbornDx and rWGS:

This clinical trial provides a unique opportunity to examine observed health outcomes, care utilization, and family resource use for infants being evaluated for a suspected genetic disorder. During the trial, charge and cost data will be collected from the total hospital bill at discharge home from the index hospitalization in which the infant is enrolled in the study. Following discharge, the parent will be contacted every 30-days to collect resource utilization related to medical visits, hospitalizations, diagnostic tests, labs, procedures, and medications administered after discharge home until one year of age corrected for prematurity. Data will also be collected on: 1) mother and father lost work days; and 2) observed health outcomes, including death, diagnoses, and the timing of diagnosis. We will use a quality of life instrument to measure parental quality of life at monthly follow-up and to infer the value parents place on avoiding adverse health conditions. We will also collect parent-reported quality of life of the infant using a visual analog scale. Health economics practice guidelines call for inclusion of such outcomes, particularly in child health intervention evaluations^{59,60}.

Assessment of SOC testing

As no infant in our trial will only receive SOC testing only (i.e., without NewbornDx and rWGS), we will estimate standard of care testing outcomes (costs, diagnostic findings, health outcomes) by using a retrospective chart review.

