In the retrospective chart review, we will collect resource utilization and health care outcome data from 300 infants born 12-18 months prior to the start of the study who had a genetic evaluation, but did not receive NewbornDx and rWGS. We chose infants born in this timeframe to minimize differences between contemporary clinical practice and clinical practice received by our retrospective cohort, hence maximizing the generalizability of our retrospective data to contemporary settings.

Simulation: Extending outcome estimates to a lifetime time horizon

Following data collection, we will use simulation modeling to estimate outcomes (cost, and health outcomes) for all strategies: NewbornDx, rWGS and standard of care diagnostic testing over a 1-year and lifetime horizon. For each strategy, the simulation model will project disorder progression based on estimated health state transition probabilities. By associating each health condition (or “health state”) with a “utility weight” (QALYs gained per year in that state) and annual cost, the simulation will track hypothetical infants and sum QALY gains and incurred costs. Repeating this process with a large number of simulated infants will yield estimated population health and cost outcomes. Costs and utility weights will be estimated from trial data, and previously published estimates, making the assumption that these values depend only on the infant’s health state and not on the diagnostic testing technology. Thus, we assume that the costs and utility weight estimates apply to infants undergoing any of the three diagnostic testing approaches.

Since NewbornDx and rWGS will identify a large number of disorders, disorders will be grouped based on estimated life expectancy and long-term severity. We will identify “disorder groups” by reviewing available data and literature on the expected outcomes of each identifiable disorder in conjunction with expert clinical judgment. We will also identify health states that appropriately represent the possible outcomes for each “disorder group” following review and synthesis of available evidence with input from our Steering Committee and DSMB.

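### The plan states no common eligibility filter, index date or case-mix adjustment for the SOC chart cohort, so case-mix can enter the cost-effectiveness comparison with SOC

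*Combined protocol and SAP*

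**What the plan says.** Section 9.4.3 states that "outcomes for standard of care will rely on retrospective chart review", and under its heading on SOC testing that "we will estimate standard of care testing outcomes (costs, diagnostic findings, health outcomes) by using a retrospective chart review". The cohort is 300 infants, born 12 to 18 months before the study starts, "who had a genetic evaluation, but did not receive NewbornDx and rWGS". The stated reason for the birth window is to keep clinical practice close to contemporary practice.

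Section 4.1 describes the same component as "A retrospective chart review of neonates with suspected genetic disorders completed at 3 sites", to be "performed under a separately submitted amendment to the central IRB". The three sites are not named. For the trial itself, section 5.4 says "Six US sites will recruit for this study".

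Trial entry is set in sections 5.1 and 5.2. Infants are inpatients under one year corrected gestational age (CGA) with signs or symptoms of a possible genetic disorder, and "enrollment is not limited to the initial hospitalization after birth, it may occur during a readmission". Exclusions include a known genetic diagnosis, a major anomaly with a prenatally detected chromosomal anomaly, and documented congenital infection. Section 5.1 also sends obvious disorders to targeted testing before enrolment. Sections 7.1 and 7.2 provide for withdrawal when a clinical diagnosis comes before the study tests are complete.

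The simulation part of section 9.4.3 applies one set of state costs and utility weights, from trial data and published estimates, to all three strategies. Transition probabilities are conditional on the strategy.

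**The concern.** The SOC contrast is a comparison with a non-concurrent external cohort. It can be read as a test effect only if the charts represent the infants who entered the trial, observed from a comparable starting point. The stated entry rules do not secure this. The trial removes several kinds of infant whom SOC diagnoses readily, or whose illness has another known cause, and no counterpart is stated for the charts. The reason given for the birth window concerns calendar time, not who was sampled.

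At stake are the one-year and lifetime cost-effectiveness endpoints and Hypothesis 2 in section 4.1, which expects NewbornDx to cost less than rWGS or SOC. The primary yield endpoints do not use the charts. The contrast between NewbornDx and rWGS is made within the same infants.

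**Working it through.** **1. The plan's own figure.** Section 9.2 gives confidence limits for a proportion with 400 infants. The Wald formula p ± z·√(p(1−p)/400) reproduces all six rows with z = 2. With z = 1.96 it reproduces every row except p = 0.30, where it gives 0.26 to 0.34 against the stated 0.25 to 0.35. That table does not bear on the SOC contrast. The 300 charts have no stated derivation. By the same formula with n = 300 and z = 1.96, the half-width is 4.0 points at 15% and 5.7 points at 50%.

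**2. The two cohorts side by side.**

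| Feature | Trial | Charts |
|---|---|---|
| Entry | Inpatient with signs or symptoms (5.1); genetics consulted as local SOC dictates (10.1.1.2) | Suspected genetic disorder (4.1); had a genetic evaluation (9.4.3) |
| Known genetic diagnosis, prenatal chromosomal anomaly, congenital infection | Excluded (5.2) | Not stated |
| Clinical diagnosis before sequencing ends | Withdrawal provided for (7.1, 7.2) | No equivalent stated |
| Start and end of observation | Enrolment at any age under one year CGA, to one year CGA (1.1, 4.3, 5.1) | 1-year outcomes (4.1); no index date stated |
| Adjustment or case-mix sensitivity analysis | None stated | None stated |

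A suspected disorder is common to both. A trial infant need not have had the genetic evaluation that brings a chart into the review. On timing, section 9.4.3 speaks of one-year outcomes after identification, but an infant enrolled at 9 months CGA is followed for 12 − 9 = 3 months. Without an index date the charts cannot be aligned to that.

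**3. Where case-mix enters.** State costs and utilities are shared, so they need not carry it. SOC diagnostic findings and health outcomes come from the charts, and transition probabilities depend on strategy. Those are the open routes. Beyond one year, section 9.4.3 takes transition probabilities from existing datasets and literature. Chart case-mix would then reach the lifetime result mainly through the diagnoses and the mix of states at one year, which is my inference from the model description.

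**4. Illustration, not an estimate.** Section 2.1 cites diagnostic yields of 15% for SOC and 44% for rWGS, a gap of 29 points. Assume that a share x of the charts are infants diagnosed by targeted SOC tests whom the trial would have excluded, and that SOC yield is 15% in the rest. Then chart yield = x + (1 − x)·0.15.

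| x (assumed) | Chart SOC yield | Apparent gap |
|---|---|---|
| 0% | 15.0% | 29.0 points |
| 5% | 19.3% | 24.8 points |
| 10% | 23.5% | 20.5 points |
| 20% | 32.0% | 12.0 points |
| 30% | 40.5% | 3.5 points |

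The sampling half-width of the 29-point gap, treating the cohorts as independent, is 1.96·√(0.44·0.56/400 + 0.15·0.85/300) = 6.3 points. At x = 10% the shift is 8.5 points, beyond that half-width, with no change in test performance.

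The shift can also run the other way. If 10% of charts were infants with congenital infection and no genetic diagnosis, chart yield would be 0.90·0.15 = 13.5% and the gap 30.5 points. The documents give neither share.

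**The case against.** The strongest reply is that the plan does not compare raw cohort means. It runs a health-state simulation, groups disorders by life expectancy and severity, and applies shared state costs. Conduct of the chart review is deferred to a separate amendment that is not among the supplied documents and may contain eligibility rules. The endpoints are secondary and the plan is descriptive. All of that is fair. But disorder grouping does not balance the mix of groups or the undiagnosed share between cohorts. Section 9.4.3, which does specify the comparison, is silent on adjustment. Its sensitivity analyses concern long-term extrapolation.

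A reader might infer more than the documents support:

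- **Different sites.** The text gives three unnamed sites against six. The three may be among the six.
- **Different ages.** Section 4.1 says neonates and section 9.4.3 says infants. The protocol also calls trial subjects neonates in places (for example, section 6.1.1), so no age restriction is established.
- **Different cost capture.** Trial costs are not only parent-reported. They include the index hospital bill and physician CPT codes, with records on request (8.2, 9.4.3). Under shared state costs, a difference in capture would not enter the cost of each state.
- **A dollar bias.** One could combine the $76,164 average NICU cost with the 40% longer stay in section 2.1. That would describe a crude mean-cost difference under an assumed case-mix gap, not the planned estimand. It would also apply a NICU average to a population that includes PICU and inpatient-floor infants.
- **No adjustment will be done.** The documents show only that none is stated.

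**Conclusion.** The point holds as a worthwhile, inexpensive improvement to the secondary economic analysis. The supplied text gives no common eligibility filter, no index date equivalent to enrolment, and no case-mix adjustment or sensitivity analysis for SOC against the trial. Following it as written lets case-mix enter the SOC diagnostic findings and the strategy-specific transition probabilities. Neither the direction nor the size of the resulting bias can be computed from the documents, and the yield table above rests on assumed shares. The conclusion assumes that the separate amendment does not already supply these elements and that first-year SOC inputs draw on the charts, as section 9.4.3 says.

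Two pairs of statements also need reconciling. One is neonates (4.1) against infants (9.4.3). The other, within section 9.4.3, is SOC costs from charts against one set of state costs from trial and published data for every strategy.

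**What to change.** In section 9.4.3 and in the chart-review amendment:

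- Apply the trial's inclusion and exclusion criteria to the charts, and define an index date equivalent to enrolment.
- Standardise or regress the SOC inputs on baseline variables available in both sources, for example gestational age, birth weight, primary system involved and age at index. Confirm first that the charts hold them, since the documents list no chart variables.
- Report the unadjusted result as a sensitivity analysis.
- Name the three chart sites. If they are trial sites, add a same-site sensitivity analysis.
- Reconcile the two pairs of statements on age label and cost source.

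Section 8.2 already collects the clinical genetic tests that would have been done without the study. These could serve as a cross-check on SOC testing, and no such use is stated.

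The cost is fewer eligible charts, wider intervals, and some extra abstraction and analysis. The chart review needs its own amendment in any case.

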3 OBJECTIVES AND ENDPOINTS

Primary Objectives	Endpoints		Endpoint Justification
To estimate the diagnostic yield of NewbornDx and rWGS in identifying genetic disorders of unknown etiology	Primary	A confirmed genetic disorder detected by NewbornDx A confirmed genetic disorder detected by rWGS	Assess diagnostic capability of the platforms
	Secondary	For diagnoses by rWGS, if trio testing was required to confirm a diagnosis	Assess need for including biological parents
To assess the clinical utility of genomic sequencing	Primary	Time from sample collection to positive test result	Assess the timeliness of an accurate result
	Primary	Clinical utility of genomic sequencing	Assess impact on care
	Secondary	If the infant does not receive a diagnosis, calculated at discharge and at 1year CGA	Assess the clinical impact of platform(s)
Secondary Objectives	Endpoints		Endpoint Justification
To examine the economic impact and health outcomes of NewbornDx and rWGS in infants compared with SOC diagnostic testing, over a one-year and lifetime horizon	Secondary	One-year cost-effectiveness of NewbornDx and rWGS compared with SOC testing	Assess economic value of alternative testing strategies
	Secondary	Lifetime cost-effectiveness of NewbornDx and rWGS, compared with SOC testing	Assess economic value of alternative testing strategies
To develop and qualitatively assess the web-based clinical reference database of supporting information for medical providers and parents	Secondary	Satisfaction of the web-based clinical reference database	Assess ease of use and usefulness of information among medical providers
Exploratory Objectives	Endpoints		Endpoint Justification
To inform the NewbornDx panel with findings from rWGS that were not identified with NewbornDx	Exploratory	Conditions detected by rWGS that were not detected by NewbornDx	Expand and improve the diagnostic accuracy of the NewbornDx panel

How endpoint(s) will be adjudicated

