Hypothesis #2: NewbornDx will be substantially less costly than rWGS or SOC testing over a one year and lifetime horizon

Hypothesis #3: Medical providers will be satisfied with the web-based clinical reference database of supporting information.

Interim analyses are not planned.

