aggregate population costs and health outcomes (QALYs) for each trial strategy; 2) rank the strategies from least to greatest aggregate population health (total QALYs); and 3) calculate incremental QALYs and costs for the second strategy (compared to the first) and for the third strategy (compared to the second). Incremental QALYs are, by our sequencing of these comparisons, non-negative. If corresponding incremental costs are likewise non-negative, an incremental cost-effectiveness ratio (ICER) (incremental costs divided by incremental QALYs) will be calculated in a similar fashion. If incremental costs are negative in either case – that is, if either strategy reduces costs while improving health relative to its comparator – we refer to this strategy as “cost-saving”.

Secondary Endpoint	Definition	Scale	Populations for which the analysis will be conducted
Satisfaction of the web-based clinical reference database	Usefulness of information Ease of use of the clinical reference database	Categorical	Medical providers who use the clinical reference database after it is built

In order to qualitatively assess the impact of the intervention, we will collect surveys from medical providers across all sites. This survey will be submitted to the IRB prior to implementation.

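### The cost-effectiveness rule compares only QALY-rank neighbours and never removes a dominated strategy, so an ICER can rest on the wrong comparator and one test-versus-SOC contrast can go unreported

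*Combined protocol and SAP*

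**What the plan says.** The cost-effectiveness paragraph of Section 9.4.3 sets out a complete procedure for both the one-year and the lifetime horizon. Step 1 produces "aggregate population costs and health outcomes (QALYs) for each trial strategy". Step 2 is to "rank the strategies from least to greatest aggregate population health (total QALYs". Step 3 is to "calculate incremental QALYs and costs for the second strategy (compared to the first) and for the third strategy (compared to the second". The reporting rule follows: "If corresponding incremental costs are likewise non-negative, an incremental cost-effectiveness ratio (ICER" is calculated; if the incremental cost is negative, that is, "if either strategy reduces costs while improving health relative to its comparator", the strategy is called cost-saving.

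Neither this section nor any other removes a strongly dominated strategy (fewer QALYs at higher cost), tests for extended dominance, or recomputes an ICER once a strategy has dropped out.

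The endpoints are worded as comparisons with SOC. Section 9.4.3 lists "One-year cost-effectiveness of NewbornDx and rWGS compared with SOC testing, from a societal perspective" together with its lifetime counterpart, and the table in Section 3 gives "Lifetime cost-effectiveness of NewbornDx and rWGS, compared with SOC testing".

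**The concern.** With three mutually exclusive strategies, an ICER is interpretable only against the next best strategy still in contention. A dominated comparator is one nobody should choose, so beating it says little about value. The written rule keeps it as the comparator. The third-ranked strategy can then show an ICER that is too low. It can also be called cost-saving because it costs less than the middle strategy, although it costs more than the lowest-ranked one.

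Separately, two adjacent comparisons among three strategies always leave one pair out. Unless SOC ranks in the middle, the omitted pair is one of the two test-versus-SOC contrasts that the endpoints name.

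The ICERs are the reported result of both economic endpoints, so an error here goes straight into the study's statement on value for money.

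**Working it through.** **Inputs.** The rule comes from Section 9.4.3. The plan states no total cost, QALY or ICER, so there is no figure to reproduce. All cost and QALY totals below are assumed for illustration.

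**Algebra.** Label the strategies 1, 2, 3 in rising QALY order, with costs C and QALYs Q. The rule reports

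- r21 = (C2 − C1)/(Q2 − Q1)
- r32 = (C3 − C2)/(Q3 − Q2)

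The direct ratio is r31 = (C3 − C1)/(Q3 − Q1) = w·r21 + (1 − w)·r32, with w = (Q2 − Q1)/(Q3 − Q1). When costs rise with QALYs, strategy 2 is extendedly dominated if r21 > r32. In that case r32 < r31, so the rule always understates the ICER of strategy 3. The condition is equivalent to C2 > C1 + r31 × (Q2 − Q1).

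**Where it starts to fail.** Assume SOC 10.00 QALYs/$50,000 and rWGS 10.10/$61,000, so r31 = 11,000/0.10 = $110,000. The NewbornDx cost above which the rule is wrong is 50,000 + 110,000 × (Q − 10):

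- at 10.01 QALYs: $51,100
- at 10.05 QALYs: $55,500
- at 10.09 QALYs: $59,900

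**Size.** SOC is 10.00/$50,000 throughout.

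| NewbornDx | rWGS | NewbornDx vs SOC, as written | rWGS vs NewbornDx, as written | rWGS after removing dominated strategies |
|---|---|---|---|---|
| 10.05/$57,000 | 10.10/$61,000 | 7,000/0.05 = $140,000 | 4,000/0.05 = $80,000 | 11,000/0.10 = $110,000 vs SOC |
| 10.01/$60,000 | 10.10/$61,000 | 10,000/0.01 = $1,000,000 | 1,000/0.09 = $11,111 | $110,000 vs SOC |
| 10.02/$65,000 | 10.10/$62,000 | 15,000/0.02 = $750,000 | −$3,000: cost-saving | 12,000/0.10 = $120,000 vs SOC |
| 10.05/$53,000 | 10.10/$61,000 | 3,000/0.05 = $60,000 | 8,000/0.05 = $160,000 | $160,000 vs NewbornDx (same) |
| 10.05/$45,000 | 10.10/$61,000 | −$5,000: cost-saving | 16,000/0.05 = $320,000 | $320,000 vs NewbornDx (same) |

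**All cost orders.** With QALYs rising 1, 2, 3, compare the ICERs the rule prints with those that remain after dominated strategies are removed:

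- Costs 2<1<3 and 2<3<1: strategy 1 is dominated and 3 versus 2 is the right comparison. The rule agrees.
- Costs 3<2<1: no ICER is printed and none is needed. The rule agrees, although strategy 2 is also called cost-saving when 3 dominates it.
- Costs 1<2<3: wrong only when strategy 2 is extendedly dominated.
- Costs 1<3<2: always wrong. Strategy 3 is called cost-saving against a dominated comparator, and its positive ICER against strategy 1 is never computed.
- Costs 3<1<2: always prints an ICER for a dominated strategy, but the verdict on strategy 3 is correct.

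**SOC contrasts.** There are six QALY orders. SOC is in the middle in two, and both SOC contrasts are then computed. In the other four one is missing; under SOC < NewbornDx < rWGS it is rWGS versus SOC.

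**Could it happen here?** Section 2.1 cites diagnostic yields of 15% for SOC and 44% for rWGS. Hypothesis #1 in Section 4.1 commits only to NewbornDx finding at least 60% of rWGS diagnoses. Assume that QALY gain is linear in yield, that NewbornDx's diagnoses are a subset of those by rWGS, and that rWGS costs more than SOC. At the 60% floor NewbornDx yields 0.60 × 44 = 26.4% and obtains (26.4 − 15)/(44 − 15) = 39% of the rWGS gain. It is then extendedly dominated once its added cost over SOC exceeds 39% of that of rWGS. At the 85–94% overlap in Section 2.2 (a share of variants, used here as a share of diagnoses) the limits are (37.4 − 15)/29 = 77% and (41.36 − 15)/29 = 91%. The documents' figures therefore leave room for either outcome.

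**The case against.** The strongest reply is that the defect is conditional, visible and recoverable. Hypothesis #2 expects that "NewbornDx will be substantially less costly than rWGS or SOC testing over a one year and lifetime horizon"; if so, and if NewbornDx ranks second in QALYs, SOC is dominated and rWGS versus NewbornDx is the correct comparison. Where dominance does occur, the output shows it: extended dominance appears as a falling sequence of ICERs ($1,000,000 followed by $11,111), and a strongly dominated middle strategy appears as a cost-saving label on the third. Step 1 gives every total, so any missing contrast is a subtraction. The synopsis also words the endpoint as a three-way comparison, which a sequential analysis addresses. These are secondary endpoints in a descriptive plan.

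Much of this stands. Hypothesis #2 concerns cost alone, is answered by the step 1 totals and is unaffected. No data are lost. The count of four in six orders is not a probability. The serious error, a flattering result for the third strategy, requires the lowest-QALY strategy to be the cheapest.

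It does not remove the point. A low NewbornDx cost is not enough without the QALY rank. With assumed totals of 10.00/$95,000 for NewbornDx, 10.05/$100,000 for SOC and 10.30/$110,000 for rWGS, NewbornDx is cheapest, yet the rule gives rWGS 10,000/0.25 = $40,000 against SOC, where the correct figure is 15,000/0.30 = $50,000 against NewbornDx. That QALY order is less plausible, but the plan does not exclude it. A reader who spots the falling sequence must still redo the analysis, and an analyst who corrects it departs from the written procedure after seeing the results.

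**Conclusion.** The concern holds. The procedure in Section 9.4.3 is explicit and complete, and followed as written it gives a wrong-comparator ICER or label whenever the middle-ranked strategy is dominated and the lowest-ranked one is cheapest. In the illustrations the understatement runs from $80,000 against $110,000 to $11,111 against $110,000, and in one case a strategy costing $120,000 per QALY against SOC is called cost-saving. These sizes rest wholly on assumed totals; the direction of the error under extended dominance follows from the algebra.

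The SOC gap is smaller: a contrast named in the endpoints that the procedure does not list as an output in four of six QALY orders, but that can be derived from the totals. This should be fixed before the economic results are known. It does not touch the primary endpoints or Hypothesis #2.

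**What to change.** In the cost-effectiveness paragraph of Section 9.4.3, after the ranking by QALYs:

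1. Remove strongly dominated strategies, then extendedly dominated ones, and state which were removed.
2. Compute each ICER against the next remaining strategy.
3. Report incremental cost and incremental QALYs for NewbornDx versus SOC and for rWGS versus SOC, at one year and over a lifetime, as the endpoints in Sections 3 and 9.4.3 are defined.
4. Name the comparator in the results whenever a strategy is called cost-saving.

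This costs a few sentences. It uses the same model outputs and needs no new data.
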